#### **4.1.1 Pharmaceutical and Therapeutic Background**

Tedizolid phosphate (SIVEXTRO®, MK-1986) is a novel oxazolidinone prodrug antibiotic that is rapidly converted in vivo by phosphatases to the microbiologically active moiety tedizolid. Tedizolid is a protein synthesis inhibitor that interacts with the 50S subunit of the bacterial ribosome. Tedizolid has bacteriostatic activity against gram-positive bacteria including common skin pathogens *Staphylococcus aureus* (both methicillin-sensitive and –resistant strains) and *Streptococcus pyogenes*, less common species causing acute bacterial skin and skin structure infections (ABSSSI), *S. anginosus*-milleri group and *Enterococcus faecalis*, and other gram-positive aerobes and anaerobes. The tablet is highly (~90%) bioavailable after oral dosing in adults, and is provided in both IV and oral formulations. Following oral administration of a single 200 mg dose to healthy adults, maximal plasma concentrations of tedizolid (approximately 2 µg/mL) are achieved approximately 3 hours after dosing when fasted; Tmax is delayed by approximately 6 hours when tedizolid phosphate is dosed with a meal; however, the AUC is unaffected by administration with or without food. Conversion of the prodrug tedizolid phosphate to the active metabolite, tedizolid, is extremely rapid, with a half-life of 10 minutes. When the drug is dosed IV, exposure peaks at the end of the 60-minute infusion period. Systemic prodrug is rarely detectable after oral dosing. The terminal half-life of tedizolid elimination is 12 hours. Exposure is generally dose-proportional in humans.

Tedizolid phosphate is approved for the treatment of ABSSSI in adults in multiple regions, including the United States and European Union (EU), but its safety and effectiveness have not been established in children and adolescents.

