#### **5.2.1.1.1 Intravenous Tedizolid Phosphate**

Flush the IV line before and after study drug administration, per standard of care. No other IV therapy should be administered concurrently with the study drug.

A detailed method for preparation of the IV dosing solution is provided in the Pharmacy Manual.

Infuse the solution for injection at a rate to deliver the desired dose in  $60\pm10$  minutes.

Dose, allowable volumes, and infusion rate required are provided in the Pharmacy Manual. Record start and stop times in the source documents and electronic case report forms (e-CRFs). Monitor the subject for at least 30 minutes post-infusion.

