#### 7.1.3.2.2 Samples

In Part A, blood samples for analysis of tedizolid phosphate and tedizolid will be collected at the following timepoints ([Figure 2](#) or [Figure 3](#)) for subjects allocated to 1 of 2 collection schemes:

Subjects who receive single-dose tedizolid phosphate IV (shown graphically in [Figure 2](#)):

1. immediately after the end of the 1-hour infusion, and at 3 and 12 hours after the start of infusion

OR

2. at 1.5, 6, and 24 hours after the start of infusion

Subjects who receive multiple-dose tedizolid phosphate IV (shown graphically in [Figure 3](#)):

1. Day 3 at end of infusion (5th dose), 3 hours after the start of the 5th infusion, and 12 hours after the start of the 5th infusion (prior to 6th dose)

OR

2. Day 3 at 12 hours after the start of the 4th infusion (prior to 5th dose), 1.5 hours after the start of the 5th infusion, and 6 hours after the start of the 5th infusion

In Part B, blood samples for analysis of tedizolid phosphate and tedizolid will be collected at the following timepoints ([Figure 4](#)) for subjects allocated to 1 of 2 collection schemes:

Subjects who receive single-dose tedizolid phosphate oral suspension (shown graphically in [Figure 4](#)):

[figure not shown]
1. at 1, 5, and 12 hours postdose

OR

2. at 3, 8, and 24 hours postdose

[figure not shown]
[Figure 2](#), [Figure 3](#), and [Figure 4](#) provide the allowed windows for collection of blood samples.

Figure 2 Pharmacokinetic Sampling Schemes for Subjects Who Receive Single-dose Tedizolid Phosphate IV

[figure not shown]
h=hour; IV=intravenous; min=minute(s); PK=pharmacokinetics

Figure 3 Pharmacokinetic Sampling Schemes for Subjects Who Receive Multiple-dose Tedizolid Phosphate

h=hour; IV=intravenous; min=minute(s); PK=pharmacokinetics

Figure 4 Pharmacokinetic Sampling Schemes for Subjects Who Receive Single-dose Tedizolid Phosphate Oral Suspension

h=hour; min=minutes; PK=pharmacokinetics; PO=oral

Note: PK samples will not be collected from subjects receiving oral suspension who vomit during and/or within 90 minutes after administration of a dose.

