#### Primary Endpoints

Pharmacokinetics: The pharmacokinetic variables for tedizolid phosphate and tedizolid (AUC0-last, AUC0-inf, Cmax, Tmax, apparent terminal t1/2) are of interest.

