#### **8.2.4.3 Pharmacokinetics**

Concentrations of tedizolid phosphate and tedizolid will be imputed as zero at time zero, where no samples were collected. Any missing postdose plasma concentrations will be treated as missing. Values below the limit of quantification (BLOQ) will be assigned a value of zero. For summary statistics of plasma concentration versus time data, at least half of the values at that timepoint must be  $>0$  in order to report a value at that timepoint. At least 2 quantifiable postdose values are required for calculation of individual pharmacokinetics. AUC will be calculated using linear up/log down trapezoidal rule.

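### The AUC rule for IV tedizolid phosphate draws a straight line across an unsampled infusion; at the protocol's 10-minute half-life, any prodrug AUC it yields is about 20-30% low

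*Combined protocol and SAP*

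**What the plan says.** The calculation rule is in Section 8.2.4.3 and covers both analytes: "Concentrations of tedizolid phosphate and tedizolid will be imputed as zero at time zero, where no samples were collected", and "AUC will be calculated using linear up/log down trapezoidal rule". Values below the limit of quantification (BLOQ) become zero, and an individual calculation needs at least 2 quantifiable postdose values.

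No scheme in Section 7.1.3.2.2 samples during the infusion. A single-dose IV subject is sampled either "immediately after the end of the 1-hour infusion, and at 3 and 12 hours after the start of infusion" (Scheme 1) or "at 1.5, 6, and 24 hours after the start of infusion" (Scheme 2). The multiple-dose schemes also have no sample inside the 5th infusion. Section 5.2.1.1.1 sets the infusion at 60 minutes, plus or minus 10.

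Section 4.1.1 says that conversion of the prodrug "is extremely rapid, with a half-life of 10 minutes".

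Section 8.2.2 names as primary "The pharmacokinetic variables for tedizolid phosphate and tedizolid", and its list includes AUC0-last and AUC0-inf. CL and Vd are defined in the same section but are not in the primary list.

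**The concern.** A trapezoid from an imputed zero to the end-of-infusion value works if concentration rises roughly linearly during the infusion. An analyte with a 10-minute half-life does not behave that way over 60 minutes, which is six half-lives. It climbs quickly and then stays almost flat. The rule therefore drops a large part of the area in the very interval where most of the prodrug's exposure occurs.

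This is an error in the estimate, not in its precision. Enrolling more subjects or collecting every planned sample does not reduce it. Under naïve pooling only one value per parameter is reported for each age group, so no confidence interval would accompany the figure. A listed primary variable could be reported with an error in a known direction.

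**Working it through.** **The plan's own AUC figures.** The documents give no figure for bias. Their only AUC calculation is the precision statement in Section 8.2.7. Using P[t(0.975, n-1) × s/√n < ln 1.4], with (n-1)s²/σ² following a chi-square distribution on n-1 degrees of freedom:

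- n = 10, SD 0.27 and 0.32: 99.9% and 97.8% (stated 99% and 97%).
- n = 6, SD 0.27 and 0.32: 78.3% and 58.7% (stated 78% and 58%).

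These reproduce and are not in dispute.

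**Inputs for the bias.** Half-life 10 min (Section 4.1.1), so k = ln 2/10 = 0.0693 per min. Infusion T = 60 min. Assumptions: one compartment, zero-order input, and an end-of-infusion sample taken on time. Concentration is in units of the steady-state level.

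**True area.**

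- End-of-infusion value: C(T) = 1 - exp(-kT) = 1 - 1/64 = 0.984.
- AUC0-inf = T = 60.0.
- Infusion part: 60 - 0.984/0.0693 = 45.8, which is 76% of the total.
- After the infusion: 0.984/0.0693 = 14.2.

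**Area under the planned rule.**

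- Infusion part as a triangle: 0.5 × 60 × 0.984 = 29.5. The shortfall is 45.8 - 29.5 = 16.3, and all of it arises here.
- Log-down or extrapolated tail: 29.5 + 14.2 = 43.7. Ratio 43.7/60 = 0.729, so AUC is 27% low and CL = dose/AUC is 37% high.
- Pooled AUC0-last ending at 1.5 h: C(1.5 h) = 0.984/8 = 0.123. The log-down area is (0.984 - 0.123)/0.0693 = 12.4, and the total is 42.0. This is 30% below the full 60.0 (CL 43% high), and 28% below the true area to 1.5 h (45.8 + 12.4 = 58.2).
- Pooled, with a BLOQ 3 h mean set to zero and joined linearly: add 0.5 × 90 × 0.123 = 5.5, total 47.5. Ratio 0.792, so AUC is 21% low and CL 26% high.

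**Sensitivity.** With a log-down or extrapolated tail, the ratio is (1 - exp(-kT)) × (0.5 + 1/(kT)). The documents give no infant half-life, so the range below is an assumption.

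| Half-life (min) | Ratio to true | AUC0-inf bias |
|---|---|---|
| 5 | 0.620 | -38% |
| 10 | 0.729 | -27% |
| 15 | 0.807 | -19% |
| 20 | 0.858 | -14% |
| 30 | 0.916 | -8% |

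At 10 minutes, infusions of 50 and 70 min give -24% and -30%. An end-of-infusion sample taken 5 min late gives -46%.

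**Set against the planned precision.** On the log scale the 27% bias is ln 0.729 = -0.32. With the plan's SD of 0.27, the expected 95% CI half-width is 2.262 × 0.27/√10 = 0.19 for n = 10 and 2.571 × 0.27/√6 = 0.28 for n = 6. The bias exceeds both.

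**Which calculation would be reached.** If every sample were quantifiable, Scheme 2 alone would give 0.122 of the true AUC, because its line runs from zero to 1.5 h. The scheme ratio would then be 0.729/0.122 = 5.98, above 2.0, and naïve pooling would follow. But the 3 h sample is 120 min, or 12 half-lives, after the end of infusion (1/4096 of peak). Scheme 2's 6 h sample is 270 min, or 27 half-lives, after its 1.5 h sample. If both are BLOQ, each subject has one quantifiable value, no individual AUC is allowed, and there is no scheme ratio to compute.

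**The case against.** **The half-life is not an infant value.** It stands in a background paragraph whose other figures come from adults. A reader might infer that prodrug AUC will be 27% low and clearance 37% high in this trial. The documents do not support so flat a statement: it is one idealised case, and the table above shows how far it moves. This objection stands, so the size must be stated conditionally.

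**The tail is not settled.** Log-down interpolation cannot use a BLOQ value set to zero, and Section 8.2.4.3 does not say what replaces it. The results of 21%, 27% and 30% reflect three readings. The 21% reading fits the plan least well, since a timepoint mean is reported only if at least half the values exceed zero. The documents do not exclude it outright.

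**Naïve pooling is not automatic.** A reader might infer that subjects who fail the 2-value rule pass to the pooled analysis. Section 8.2.4.3 gives only the scheme ratio as a trigger, and Section 7.1.3.2.1 only permits pooling for Groups 1-3. On the literal text, the prodrug AUC could simply be missing. The assay limit is not given, so neither outcome is established.

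**The consequence is limited.** A reader might infer that dose selection is affected. Tedizolid is the active moiety, Section 4.2.3.3 ties the importance of AUC to efficacy, and Section 4.2.2 based the doses on a population PK model. Nothing in the documents shows a decision that turns on prodrug AUC. CL and Vd are not listed as primary and are calculated only as appropriate.

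**The closed form has weaknesses.** It rests largely on one sample, and a sample 5 min late reads 29% low (2^-0.5 = 0.71) unless corrected. Its rate constant comes from different subjects, because the end-of-infusion and 1.5 h samples belong to different schemes. Hence the actual sampling times and the stated assumption in the fix.

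None of these objections gives a reading in which an AUC formed from an on-time end-of-infusion sample and the pooled 1.5 h value is unbiased.

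**Conclusion.** The point holds conditionally. At the documents' 10-minute half-life and a 60-minute infusion, an IV tedizolid phosphate AUC from an on-time end-of-infusion profile or from the pooled profile would be about 20-30% low, and any CL from it about 26-43% high. Over assumed half-lives of 5 to 30 minutes, the AUC0-inf bias runs from -38% to -8%. It is always downward under these conditions, and sample size cannot correct it. If the 3 h and 6 h prodrug samples are BLOQ, the plan leads either to no prodrug AUC or to a pooled value carrying this bias.

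The result assumes one-compartment prodrug kinetics. It does not extend to tedizolid AUC, to dose selection or to the precision figures in Section 8.2.7. It is a low-severity correction, worth making because prodrug AUC is a listed primary variable and the remedy is cheap.

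**What to change.** In Section 8.2.4.3, exclude IV tedizolid phosphate from the linear trapezoid over the infusion and choose one of the following.

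1. **Zero-order-input formula.** AUC0-inf = C(end of infusion) × T/(1 - exp(-kT)), with T the actual infusion duration and k from the pooled end-of-infusion and 1.5 h data at their actual times. Multiply a late end-of-infusion value by exp(k × delay). State the one-compartment assumption. Without a delay, the result depends only moderately on k: T/(1 - exp(-kT)) is 1.00 h at a 5-minute half-life and 1/0.875 = 1.14 h at 20 minutes.
2. **Population PK model.** Name it as the source of prodrug AUC. At present Section 8.2.4.3 makes it optional.
3. **Limited reporting.** Give end-of-infusion prodrug concentrations only, and drop prodrug AUC, CL and Vd, amending the primary list in Section 8.2.2.

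For options 1 and 2, also say what is reported when no individual prodrug AUC meets the 2-value rule, and align Sections 7.1.3.2.1 and 8.1.1.2. Leave the tedizolid rule unchanged.

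The cost is a few sentences and a short calculation. Infusion start and stop times are already recorded, and no sample or procedure changes. Option 1 carries the one-compartment assumption and relies mainly on a single timepoint. Option 3 avoids both but gives up a listed endpoint.

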### **IV Administration (Group 1 [Cohort 1 and 2 Combined], Group 2, and 3)**

A non-model-based GM of the AUC and  $C_{max}$  of tedizolid phosphate and its active metabolite, tedizolid after administration (5th dose or first dose on Day 3 for multiple-dose groups) will be calculated for each PK sampling scheme by age and dose (if dose adjusted at interim analysis) group. A ratio of non-model based GM between two PK sampling schemes will also be calculated by age group. If the ratio is greater than 2.0 or less than 0.5 for an age group, the naïve-pooled approach will be used to summarize the PK. In this approach, only one value for each PK parameter will be estimated for each age group, as specified in Section 7.1.3.2.1. If the ratio of non-model based GM between two PK sampling schemes is within 0.5 and 2.0 for an age group, individual PK parameter values will be estimated. An ANOVA model including factor for Group/Cohort will be used to analyze log transformed PK parameter values of tedizolid phosphate and tedizolid. Point estimates and two-sided 95% confidence intervals will be constructed for the GM in pediatric subjects, by age group, for AUC and  $C_{max}$  of tedizolid phosphate and tedizolid.

### **Oral Administration (Groups 4, 5, and 6)**

The AUC of tedizolid phosphate and tedizolid, administered as oral suspension will be calculated using naïve-pooled approach as specified in Section 7.1.3.2.1. Only one value for AUC will be estimated for each age group.

The bioavailability will be estimated by dividing the naïve-pooled AUC from oral administrated subjects by the estimated AUC from IV administrated subjects, for each age

group. If the ratio of non-model-based GM between two PK sampling schemes is between 0.5 and 2.0, then GM AUC estimate from ANOVA model will be used as the estimated AUC from IV administrated subjects. Otherwise, the naïve-pooled AUC estimate from each age group will be used. An average bioavailability will also be reported across age groups.

For IV administrated subjects with available individual PK parameter estimates, individual values will be listed for each PK parameter by age group, dose and PK sampling scheme, and the following (non-model-based) descriptive statistics will be provided: N (number of subjects with non-missing data), arithmetic mean, standard deviation, arithmetic percent CV (calculated as  $100 \times \text{standard deviation}/\text{arithmetic mean}$ ), median, minimum, maximum, GM, and geometric percent CV (calculated as  $100 \times \text{sqrt}[\exp(s^2) - 1]$ , where  $s^2$  is the observed variance on the natural log-scale).

The effects of body weight and renal function on the PK parameter values may be graphically analyzed if appropriate. These data may be used in a population PK analysis.

### **8.2.5 Multiplicity**

Since there are no prespecified hypotheses, no adjustments for multiplicity will be made.

### **8.2.6 Interim Analysis for Potential Dose Adjustment**

The initial dose chosen at the time of the Initial Protocol has been modified to 3 mg/kg in Amendment 01, prior to enrollment of the first subject (see Section 4.2). Interim analyses are planned to evaluate the PK (eg,  $AUC_{0-\infty}$ ) and safety profile and make dose adjustment, if deemed appropriate. Interim analyses will be conducted after PK data are available as follows:

1. The first 5 subjects from Group 1 (Cohort 1 and 2 combined), and
2. The first 6 subjects from Group 2, and
3. The first 6 subjects in Group 3.

Non-model-based summary statistics (including N, arithmetic mean, standard deviation, arithmetic percent CV, median, minimum, maximum, geometric mean, and geometric percent CV) of  $AUC_{0-\infty}$  will be provided for each age group.

### **8.2.7 Sample Size and Power Calculations**

#### Pharmacokinetics:

It is assumed that the variabilities of AUC and volume of distribution [Vd] of pediatric subjects are the same as those of adults as observed in pooled historical adult subjects from Studies MK-1986-008 (TR701-107) and MK-1986-031 (TR701-123).

Assuming the between-subject standard deviations of  $\log(AUC)$  are 0.27 and 0.32 for tedizolid phosphate and tedizolid, respectively, with 10 completers in Group 1 (Cohort 1 and Cohort 2 combined), there are 99% and 97% probabilities that the 95% CI of GM is within 60% and 140% of the GM estimate; with 6 completers in Group 2 Cohort 1, there are 78% and 58% probabilities that the 95% CI of GM is within 60% and 140% of the GM estimate.

Assuming the between-subject standard deviations of  $\log(Vd)$  are 0.28 and 0.29 for tedizolid phosphate and tedizolid, respectively, with 10 completers in Group 1 (Cohort 1 and Cohort 2 combined), there are 99% and 99% probabilities that the 95% CI of GM is within 60% and 140% of the GM estimate; with 6 completers in Group 2 Cohort 1, there are 74% and 70% probabilities that the 95% CI of GM is within 60% and 140% of the GM estimate.

Power calculations are not provided for subjects who receive multiple doses of tedizolid phosphate; the sample size was based on pragmatic considerations.

## **9.0 LABELING, PACKAGING, STORAGE AND RETURN OF CLINICAL SUPPLIES**

### **9.1 Investigational Product**

The investigator shall take responsibility for and shall take all steps to maintain appropriate records and ensure appropriate supply, storage, handling, distribution and usage of investigational product in accordance with the protocol and any applicable laws and regulations.

Clinical Supplies will be provided by the Sponsor as summarized in [Table 6](#).

Clinical supplies will be packaged to support enrollment and replacement subjects as required. When a replacement subject is required, the Sponsor or designee needs to be contacted prior to dosing the replacement supplies.

The investigational trial drug is tedizolid phosphate, also known as SIVEXTRO®.

#### *Intravenous Form*

Tedizolid Phosphate is formulated as a sterile lyophilized powder for injection for IV administration. Tedizolid Phosphate for Injection, 200 mg/vial, consists of Tedizolid Phosphate, mannitol, and sodium hydroxide that are lyophilized in a clear glass vial. The resulting drug product is a white to off-white cake that results in a clear light-yellow solution after reconstitution.

Tedizolid Phosphate for Injection, 200 mg/vial will be manufactured according to Good Manufacturing Practice (GMP) requirements. Additional information is provided in the Pharmacy Manual.

#### *Oral Suspension Form*

Tedizolid Phosphate Powder for oral suspension is white to off-white powder for constitution into suspension for oral administration. The product is supplied in clear glass bottles, and includes the following inactive ingredients: potassium sorbate, silicon dioxide, succinic acid, sucrose, and xanthan gum. Additional information is provided in the Pharmacy Manual.

Table 6 Product Descriptions

Product Name & Potency	Dosage Form	Source/Additional Information
Tedizolid phosphate 200 mg	Lyophilized Powder for injection	Provided centrally by the Sponsor
Tedizolid phosphate (20 mg/mL)	Powder for Oral Suspension	Provided centrally by the Sponsor

All supplies indicated in [Table 6](#) will be provided per the “Source/Additional Information” column depending on local country operational requirements.

Any commercially available product not included in [Table 6](#) will be provided by the trial site, subsidiary or designee. Every attempt should be made to source these supplies from a single lot/batch number. The trial site is responsible for recording the lot number, manufacturer, and expiry date for any locally purchased product as per local guidelines unless otherwise instructed by the Sponsor.

## **9.2 Packaging and Labeling Information**

Clinical supplies will be affixed with a clinical label in accordance with regulatory requirements.

No kitting is required.

## **9.3 Clinical Supplies Disclosure**

This trial is open-label; therefore, the subject, the trial site personnel, the Sponsor and/or designee are not blinded. Treatment (name, strength or potency) is included in the label text; random code/disclosure envelopes or lists are not provided.

Section 5.8 outlines the criteria for allowing subjects who are discontinued from treatment to continue to be monitored in the trial.

## **9.4 Storage and Handling Requirements**

Clinical supplies must be stored in a secure, limited-access location under the storage conditions specified on the label.

Receipt and dispensing of trial medication must be recorded by an authorized person at the trial site.

Clinical supplies may not be used for any purpose other than that stated in the protocol.

## **9.5 Discard/Destruction>Returns and Reconciliation**

The investigator is responsible for keeping accurate records of the clinical supplies received from the Sponsor or designee, the amount dispensed to and returned by the subjects and the amount remaining at the conclusion of the trial. For all trial sites, the local country Sponsor

personnel or designee will provide appropriate documentation that must be completed for drug accountability and return, or local discard and destruction if appropriate. Where local discard and destruction is appropriate, the investigator is responsible for ensuring that a local discard/destruction procedure is documented.

